The primary treatment for BCLM remains chemo-therapy and, more recently, targeted immunotherapy. Liver metastases from other primary tumors, such as colorectal cancers, are routinely resected as part of standard management. Breast cancer rarely develops isolated liver metastases because neo-plastic cells at this stage have often already reached systemic circulation with the possibility of further localization, unlike colon cancer, where the liver, through the portal system, is the first organ to be colonized. Therefore, the role of liver resection in BCLM remains controversial [6-8].

Hepatic resection and/or ablation was not associated with a survival advantage in some studies [9], whilst in other disclosed a remarkable improvement as compared to systemic treatment alone [10,11], thus indicating surgical intervention as suggested in highly selected patients with the goal of providing time off of systemic chemotherapy.

Our study thus aims to provide further insights in this complex and still unclear field of research.

OBJECTIVES

Primary Objective

Primary aim of the study is to compare the efficacy of liver resection vs. medical therapy alone in Breast Cancer Liver Metastasis (BCLM) patients.

Secondary Objectives

- To assess the recurrence rate after liver resection or medical treatment alone;
- To assess Recurrence free survival (RFS);
- To assess potential factors involved in both overall survival and RFS.

METHODS

Study design

Multicenter observational ambispective study.

Population

We will enroll all patients with BCLM underwent liver resection or medical treatment alone afferent to the Fondazione Policlinico Gemelli IRCSS of Rome (Italy), and other 8 International centers (as detailed in the attached document), following the inclusion and exclusion criteria hereafter detailed.

Study duration

The study will overall last 68 months since the approval of the present protocol by the sponsor center institutional review board (IRB), i.e. Fondazione Policlinico Gemelli IRCSS of Rome (Italy), and of all the satellite centers. The prospective enrolment of patients will last till the December 31, 2023 and follow-up phase will last for other 5 years, till December 31, 2028.

Study phases

The study foresees two distinct phases:

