- **I phase (only retrospective phase)** → it will cover all patients underwent to either medical treatment or surgery for which all data are available, with a follow up of 5 years at March 31, 2023. We will retrieve all patients data from January 1994 till March 31, 2018. At the end of “phase I”, we foresee an “ad interim” analysis.
- **II phase (ambispective)** → we will further include all patients retrieved from the archives between April 1, 2018 and the April 30, 2023, as well as all prospectively enrolled patients till December 31 2023, so that the last patient enrolled will end the 5-years follow-up phase within December 31, 2028.

Inclusion criteria

- Age >18 years old;
- Presence of BCLM;
- BCLM and extra-hepatic disease;
- Any treatment;
- Ability to understand and sign the informed consent.

Exclusion criteria

- Inability to provide the informed consent;
- Patients who underwent Best Supportive Care or palliation.

Variables and procedures

The following data will be retrieved from medical archives of each participating center for all retrospectively enrolled patient.

Prospectively enrolled patients' data will instead be collected in the related medical record and reported, alongside all other patients' data, in an electronic dataset protected by password and accessible only to the PI and the co-investigators, and to any other person authorized by PI.

In depth, the following data will be included:

- Anonymized ID;
- Demographic and anthropometric data (e.g., age, sex, BMI, etc..);
- Name of the participating center;
- ER, PR and HER2 status,
- Presence of BRCA1-2 mutation,
- Neoadjuvant-radiotherapy,
- Neoadjuvant endocrine therapy,
- Neoadjuvant-chemotherapy,
- Neoadjuvant-anti-HER2,
- Date of breast surgery,
- Breast tumor T and N,
- Adjuvant radiotherapy,

- Ad-endocrine therapy, Ad-chemotherapy, and Ad-anti-HER2,
- Date of liver metastasis diagnosis,
- Date of liver surgery,
- Liver surgery,
- Liver resection major/minor (Segmental or wedge resection or Left Lateral),
- R status,
- Number of liver metastasis,
- Size of the bigger lesion (mm),
- Distribution (uni or bilobar),
- Postoperative morbidity,
- Hormone receptor expression in the liver metastasis (ER+, PR+),
- Extra-hepatic disease,
- Site of Extra-hepatic disease,
- Mortality and cause;
- Date of death or last FU observation,
- Recurrences,
- Site of recurrences,
- Date of recurrences.

ENDPOINTS

Primary endpoint

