The primary endpoint is to analyze the efficacy of liver surgery as compared to medical therapy alone in terms of 5-years overall survival in patients with breast cancer who underwent to liver resection or medical therapy alone.

Secondary endpoints

- Recurrence rate;
- Post-operative mortality (in patients who underwent to surgical treatment).
- Post-operative complication (in patients who underwent to surgical treatment).
- To assess potential predictive factors of 5-years overall survival in patients with breast cancer who underwent to either liver resection or medical therapy alone.
- To assess recurrence free survival (RFS) of liver surgery as compared to medical therapy alone in terms of 5-years overall survival in patients with breast cancer who underwent to liver resection or medical therapy alone.
- To assess potential predictive factors of 5-years RFS in patients with breast cancer who underwent to either liver resection or medical therapy alone.

STATISTICAL ANALYSIS PLAN

Sample size calculation

The sample size was computed based on the assessment of an improvement in the OS of patients surgically treated as compared to systemic therapy alone.

Based on the evidence from Ruiz and colleagues [10], which reported a 5-years OS of 24% among women treated only with medical therapy and of 69% among those surgically treated, we hypothesize to obtain in our study sample an OS of 60% in the treated group and of 25% in the systemic therapy group.

As such, considering a treatment/control ratio of 0.15/0.85, a two-sided log-rank test with an overall sample size of 117 subjects (99 in the systemic therapy group and 18 in the surgical treatment group) achieves 90% power at a 0,05 significance level to detect a hazard ratio of 0,37 when the proportion of 5-year OS in the control group is 25%. The study will consider a time-window of 30 years of total enrolment (from 1994 to 2023) and a follow-up period of 5 years, for a total time of 35 years. The accrual pattern across time periods is uniform (all periods equal). We expect no subjects drop out both in the control group and treatment groups. The expect no. of events is of 96,5 in the control group and 14,3 in the treatment group. The sample size calculation was performed with PASS2022 v22.0.3 [12,13]. Such sample size estimation is consistent with the disease specific metastasis prevalence and on the no. of involved centers. In fact, we overall expect to include in both retrospective and

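### The inclusion criterion on treatment is wider than the two-group comparison, and no data item identifies patients given ablation or another non-resection liver-directed treatment

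*Protocol*

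**What the plan says.** - **Population (Methods).** "We will enroll all patients with BCLM underwent liver resection or medical treatment alone", subject to the inclusion and exclusion criteria that follow.
- **Inclusion criteria.** One line reads "Any treatment", with no qualifier.
- **Exclusion criteria.** The only exclusion based on treatment is "Patients who underwent Best Supportive Care or palliation".
- **Study phases, phase I.** "it will cover all patients underwent to either medical treatment or surgery for which all data are available". Here medical treatment is not qualified as being given alone.
- **Primary endpoint.** 5-year overall survival is compared "in patients with breast cancer who underwent to liver resection or medical therapy alone".
- **Background.** A third kind of treatment is acknowledged: "Hepatic resection and/or ablation was not associated with a survival advantage in some studies".
- **Variables and procedures.** The liver-treatment items are liver surgery, its date, the type of resection ("Liver resection major/minor (Segmental or wedge resection or Left Lateral") and R status. There is no item for ablation or any other non-resection liver-directed treatment. The systemic-therapy items are labelled neoadjuvant or adjuvant and are listed around breast surgery. None names the systemic therapy given for the liver metastases.

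**The concern.** The Population paragraph narrows entry to two treatments and then hands over to a criterion that lifts the restriction. Ablation plus systemic therapy satisfies every listed criterion, yet it is neither a resection nor medical therapy alone.

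Nine centres (the sponsor centre and 8 others) will abstract records going back to 1994. Without a rule, each can treat such a patient differently, and the listed variables would not show which choice was made. What is at stake is the meaning of the control group. It could vary by centre and, if it takes in selected, locally treated patients with better survival, the estimated benefit of resection would be diluted. Eligibility wording and the list of variables to abstract are fixed in the protocol, and an analysis plan cannot supply a variable that was never collected.

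**Working it through.** **1. The text side by side.** Take a patient with liver metastases treated by ablation and systemic therapy.

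| Source in the protocol | Result for this patient |
|---|---|
| Inclusion criteria | Admitted: any treatment qualifies |
| Exclusion criteria | Not excluded: not best supportive care or palliation |
| Population, primary objective, primary endpoint | Fits neither group |
| Phase I description | Unclear: had medical treatment, but not only that |
| Data list | No item for the ablation; liver surgery may be recorded as yes or no |

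Three outcomes are compatible with this text: control group, surgical group, or not enrolled.

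**2. The plan's own figures.** Inputs from the sample size section: 5-year overall survival 60% and 25%, allocation 0.15/0.85, 117 patients, 30 years of uniform accrual plus 5 years of follow-up, no dropout.

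- Hazard ratio = ln(0.60)/ln(0.25) = 0.3685; stated 0.37.
- Yearly hazards, exponential: control −ln(0.25)/5 = 0.2773; surgical −ln(0.60)/5 = 0.1022.
- Probability of an event = 1 − [exp(−5λ) − exp(−35λ)]/(30λ): control 0.9700, surgical 0.8134.
- Expected events: 117 × 0.85 × 0.9700 = 96.5 and 117 × 0.15 × 0.8134 = 14.3. Both match the protocol.

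The hazard ratio and events reproduce, so 60% versus 25% is a sound starting point for the illustration.

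**3. Illustration of attenuation.** The documents give neither the frequency of such treatments nor survival after them, so both are assumed. Let p be their share of the control group and s their 5-year survival.

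Control survival = 0.25(1 − p) + s·p; 5-year hazard ratio = ln(0.60)/ln(control survival).

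| p | s | Control 5-year survival | 5-year hazard ratio |
|---|---|---|---|
| 0 | – | 25.0% | 0.37 |
| 10% | 25% | 25.0% | 0.37 |
| 10% | 50% | 27.5% | 0.40 |
| 10% | 60% | 28.5% | 0.41 |
| 20% | 25% | 25.0% | 0.37 |
| 20% | 50% | 30.0% | 0.42 |
| 20% | 60% | 32.0% | 0.45 |

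This is the ratio of cumulative hazards at 5 years. A mixed control group does not have proportional hazards, so a Cox estimate would differ somewhat.

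**4. Power at the expected size.** Take the least favourable row (hazard ratio 0.448, control survival 32%) with 700 patients, 15% surgical.

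- Events by 5 years: 595 × 0.68 + 105 × 0.40 = 404.6 + 42.0 = 446.6.
- Schoenfeld: √(446.6 × 0.15 × 0.85) × |ln 0.448| = 7.55 × 0.802 = 6.05; 6.05 − 1.96 = 4.09, so power exceeds 99.9%.

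At the minimum of 117 patients the same contamination would matter: simulated power over the full follow-up falls from about 94% to about 70% with a 20% share at 60% survival. The protocol expects about six times that number (700/117 = 6.0).

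**The case against.** The strongest reply is that the Population paragraph is itself an entry condition. On that reading the criterion means any form of resection or medical therapy, and an ablated patient, not having had medical therapy alone, is simply outside the study. The two-group limit recurs in the objective, the phase I description and the endpoints. This reading is tenable. But the inclusion list does not say so, and a centre that screens by the list will enrol these patients.

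A reader might go further and infer that such patients are coded as medical therapy alone. The protocol states no such rule. A recorded absence of liver surgery would put them there, but an operative ablation could equally be entered as liver surgery, since surgery and resection type are separate items.

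A reader might also infer that, once entered, they could never be removed. That is too strong as well: the medical archives remain available, so the cases could be found by going back to source, though not from the listed variables.

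Finally, the attenuation may be nil. If these patients survive no better than those on medical therapy, the control group's survival does not change, and the Background itself cites studies without a survival advantage for resection and/or ablation. This stands, and it is why the range starts at 0.37.

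**Conclusion.** The point holds as an inconsistency in eligibility combined with a gap in the data list. The criterion conflicts with the Population paragraph, primary objective and primary endpoint. The protocol does not say how patients with other liver-directed treatment are identified or classified, and the listed variables cannot settle it.

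The likely consequence is a control group that depends on the centre, with some attenuation of the primary contrast if these patients survive longer and are counted as controls. Its size cannot be derived from the documents. The range of 0.37 to 0.45 rests on the assumed shares and survival, on the planned 60% versus 25%, and on such patients entering the control group. Power is not the issue at 675–720 patients. The change should be made because it is cheap and protects the definition of the primary comparison.

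**What to change.** 1. Reword the criterion to agree with the Population paragraph: liver resection with or without systemic therapy, or systemic therapy alone, for the liver metastases.
2. Add one data item: non-resection liver-directed therapy (yes/no, type, date).
3. Keep patients whose initial treatment for the liver metastases was such a procedure out of the primary two-group comparison and describe them separately.
4. State one rule, applied at every centre, for classifying patients who had resection combined with ablation.
5. Add a sensitivity analysis for patients who received liver-directed therapy later. Step 3 alone leaves them in the group of their initial treatment.

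The cost is one reworded criterion, one more chart-review item per patient and a modest loss of patients from the primary comparison.

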prospective phase 75-80 patients/center, for overall sample of 675-720 patients. Particularly, the retrospective phase, which will include patients till 2017 will consist of about 500 patients, already consistent with the sample size estimate provided, whilst the other will pertain to the period 2018-2023.

Statistical analysis

The sample will be described in its clinical and demographic characteristics by descriptive statistics techniques. In depth, qualitative data will be expressed as absolute and relative percentage frequency, whilst quantitative variables either by mean and standard deviation (SD) or median and interquartile range (IQR), as appropriate. To verify the Gaussian distribution of quantitative variables, the Shapiro-Wilk test will be applied.

Missing values, as <5% in all cases, were treated by *imputeR* package, using multiple imputation with Lasso Regression methods centered on the mean as for quantitative data, whilst classification trees for imputation by “rpartC” function, centered on the mode, i.e. most represented class object, were applied on qualitative data [14].

Between groups differences were analyzed by either the Chi squared test or the Fisher-Freeman-Halton test for qualitative data, whilst either the Student’s t test or non-parametric Mann-Withney U test will be applied on quantitative data, as appropriate.

Differences between groups will be further exemplified by clustered violin plots or plots describing pre-post variation in individual groups. Such plots will be produced with the R packages “ggplot2”, “ggstatsplot”, “ggpubr”, “ggprism”, and “ggsignif” [15-19].

OS will be calculated from the date of treatment initiation through the date of death from any cause; subjects alive at the last follow-up will be censored. Overall survival and RFS probabilities at 5 years will be estimated using the Kaplan Meier method and compared by the log-rank test. The KM curve will also be reported. The analysis will be performed with the R package “*ggplot2*” and “*survminer*” R packages [15,20].

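### The consent criteria are not limited to prospective patients; if consent is sought in 2023, they conflict with the retrospective cohort and the deaths that the 5-year survival comparison needs

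*Protocol*

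**What the plan says.** Under Population, patients from the sponsor centre and eight other centres are enrolled "following the inclusion and exclusion criteria hereafter detailed". One list follows, with no separate version for archive patients. Inclusion criteria contains "Ability to understand and sign the informed consent"; Exclusion criteria contains "Inability to provide the informed consent".

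Study phases describes Phase I as purely retrospective: "We will retrieve all patients data from January 1994 till March 31, 2018", "with a follow up of 5 years at March 31, 2023", restricted to patients with complete data and ending in an interim analysis. Phase II adds "all patients retrieved from the archives between April 1, 2018 and the April 30, 2023" as well as prospective patients to the end of 2023.

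The primary endpoint is 5-year overall survival (OS), surgery against medical therapy alone. Statistical analysis counts OS from the start of treatment to death from any cause and compares the groups by Kaplan-Meier and log-rank test. Sample size calculation assumes "an OS of 60% in the treated group and of 25% in the systemic therapy group", a 0.15/0.85 split, and 96.5 + 14.3 expected deaths among 117 subjects. It adds that "the retrospective phase, which will include patients till 2017 will consist of about 500 patients".

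**The concern.** A patient who died before being approached cannot sign a form. If the consent lines mean a signature obtained for this study, they make survival to the date of approach a condition of entry. For Phase I that date would fall at least five years after treatment, so the condition overlaps with the primary endpoint itself.

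Eligibility decides who is counted in the 5-year OS comparison. Nine centres have to turn these two lines into a practical rule for archive records. If some drop deceased patients and others keep them, the survival estimates reflect the consent procedure as well as the treatment. Phase I supplies about 500 of the 675 to 720 patients expected and feeds the interim analysis.

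**Working it through.** **1. Scope of the lines.** Population sends every patient to the same list, and neither consent line mentions prospective enrolment. Variables and procedures does treat archive and prospective patients separately, but only for data collection.

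**2. Date of consent.** None is given. Study duration sets 68 months from approval, ending December 31, 2028. Counting back 60 months gives December 31, 2023, and a further 8 months gives April 30, 2023. A form specific to this study would therefore plausibly be signed after March 31, 2023. This supports the assumption but does not establish it.

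**3. The protocol's expected deaths.** Assume exponential survival, uniform entry over 30 years, 5 more years of follow-up and no dropout.
- Medical hazard L = -ln(0.25)/5 = 0.2773; surgical hazard 0.37 × 0.2773 = 0.1026.
- Probability of death = 1 - [exp(-5L) - exp(-35L)]/(30L) = 0.970 medical, 0.814 surgical.
- 117 × 0.85 = 99.45 and 117 × 0.15 = 17.55, giving 96.5 and 14.3 deaths. Both match the stated figures.
- Together 110.8/117, or about 95% of subjects. The plan counts on deceased patients being in the data.

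**4. Endpoint events at risk of exclusion in Phase I.** Inputs: about 500 patients, split 425 medical and 75 surgical, with 5-year OS of 25% and 60%. No hazard model is needed.
- Dead within 5 years: 425 × 0.75 + 75 × 0.40 = 318.75 + 30 = 348.75, about 349.
- Alive at 5 years: 106.25 + 45 = 151.25.
- With a surgical share of 10% or 30% (assumed range), 142.5 or 177.5 are alive at 5 years, so 357.5 or 322.5 are dead.

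The figure of 500 is given for patients to 2017, while Phase I runs to March 2018. It is used here as it stands.

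**5. Direction of bias.** These are illustrations. They use a constant hazard (0.2773 medical; -ln(0.60)/5 = 0.1022 surgical) and uniform entry. The assumed true values are 25% and 60%, a gap of 35 points.

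The Phase I share still alive on March 31, 2023 is a = [exp(-5L) - exp(-29.25L)]/(24.25L) = 0.0371 medical, 0.2218 surgical.

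- *Phase I, all survivors enter but only a share f of the dead.* OS = [a + f(S - a)]/[a + f(1 - a)], with S the true 5-year OS. For f = 0.10: 43.8% and 86.7%, gap 43 points. For f = 0.75: 25.9% and 62.8%, gap 37 points. The values of f are not from the protocol.
- *Phase II archive, literal rule, consent on April 30, 2023.* Entry spans 61 months (T = 5.083 years). Alive share (1 - exp(-LT))/(LT) = 0.536 and 0.780. OS among those alive, with no allowance for late entry, is 0.25/0.536 = 46.6% and 0.60/0.780 = 76.9%, gap 30 points.
- *Phase I, all the dead enter under a waiver but only 70% of the living sign (illustrative).* OS = (S - 0.3a)/(1 - 0.3a): (0.25 - 0.0111)/0.9889 = 24.2% and (0.60 - 0.0665)/0.9335 = 57.1%, gap 33 points. At 50% signing the gap is about 31 points.

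The gap can widen or narrow, and OS levels can be overstated or understated.

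**The case against.** The strongest reply is that the document shows what is meant. It collects date and cause of death, describes archive retrieval separately from prospective collection, and expects 110.8 deaths among 117 subjects. The removed pages may hold a consent waiver. The criteria could also refer to capacity, or to research consent given at treatment; on either reading, patients who died later are not barred. Finally, Phase I is limited to patients with complete data, and enrolment is subject to the criteria, so a criterion that narrows the set does not by itself contradict the retrieval rule.

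Most of this stands. The intention is clear, a waiver may exist, and the conflict does depend on the consent date. It lies in combining a consent rule that could remove the dead with an endpoint and a sample size that need them.

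A reader might go further and infer that Phase I will contain no deaths, with 5-year OS of 100% in both groups. That would follow only if every centre applied the literal reading with consent in 2023, and the protocol's own expected deaths show that this is not planned. Nor can one infer that OS would always be overstated: the waiver scenario above understates it.

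The reply leaves the wording unresolved. Even with a waiver elsewhere, two unrestricted criteria would disagree with it unless they refer to it.

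**Conclusion.** The point holds as an inconsistency in the eligibility wording. Given study-specific consent at or after March 31, 2023, the two lines bar deceased archive patients and so conflict with the Phase I cohort and with the deaths on which the survival comparison depends. About 349 of about 500 retrospective patients would be the endpoint events at risk (about 323 to 358 for a surgical share of 30% down to 10%). That is an upper bound under the literal reading, not a forecast. The likelier harm is uneven application across centres, whose size cannot be derived from the protocol and whose effect on the treatment gap has no fixed sign. The wording should be corrected because it governs entry to the primary analysis and is cheap to change.

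**What to change.** - Limit both consent lines to prospectively enrolled patients.
- State that archive patients enter under the route approved by the ethics committees, with a cross-reference if that route is already described elsewhere, and apply it so that entry does not depend on vital status.
- Where a centre's ethics committee requires consent from living archive patients, report the numbers screened, included and refused by vital status and treatment group for each centre, and run a sensitivity analysis for that selection. Admitting the dead without consent while asking the living to sign would otherwise still tie entry to survival.

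The cost is a wording amendment, confirmation of the ethics route, and a little extra reporting with one sensitivity analysis where it applies. The endpoint, sample size and main analysis stay as they are.

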To assess potential prognostic factors of 5-year RFS and OS, both univariable and multivariable Cox proportional hazards regression models will be fitted, and hazard ratios (HR) and 95% confidence intervals (CI) consequently reported. The proportionality of the hazards will be assessed by visual inspection of the hazards and Schoenfeld residuals. In case of doubtful proportionality, Cox weighted regression models will be fitted. “*survival*” and “*coxphw*” R packages will be used for the whole analysis [21-24]. The predictors to be included in the multivariable model will be selected on the basis of univariable analysis ($p < 0.05$ or suggestive, i.e. $0.05 \leq p < 0.10$) and expert opinion, also considering the possibility of overcoming the rule of 10 events per variable (EPV) [25,26]. Statistical significance will be set at a p-value < 0.05 . Suggestive p-values will be further reported ($0.05 \leq p < 0.10$). All analyses will be performed with R software version 4.2.0 (CRAN ®, R Core 2022) [27].

References

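### The data list names no baseline performance status or comorbidity measure, so the non-randomised comparison of resection with medical therapy cannot be adjusted directly for patient fitness

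*Protocol*

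**What the plan says.** The primary objective is to "compare the efficacy of liver resection vs. medical therapy alone" in breast cancer liver metastasis. The design is observational and ambispective, so treatment is not allocated by the study. The background text before the objectives reads the literature as "thus indicating surgical intervention as suggested in highly selected patients", without naming the criteria by which patients are selected.

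Under Variables and procedures the list opens with "In depth, the following data will be included". The patient's general condition appears only as "Demographic and anthropometric data (e.g., age, sex, BMI, etc". The other items cover centre, receptor and BRCA status, breast tumour stage and treatment, number, size and distribution of liver metastases, extra-hepatic disease, details of liver surgery, postoperative morbidity, recurrence and death. Performance status, comorbidity and frailty are not named.

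The only eligibility rule that touches on fitness excludes "Patients who underwent Best Supportive Care or palliation". Under Statistical analysis, OS and RFS "will be estimated using the Kaplan Meier method and compared by the log-rank test". The adjusted analysis is a multivariable Cox model for prognostic factors: "The predictors to be included in the multivariable model will be selected on the basis of univariable analysis" and expert opinion.

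**The concern.** A patient must be fit enough for major surgery to have a liver resection; drug treatment does not demand this to the same degree. Patients who were too unfit for hepatectomy but received drugs remain in the medical group. If such patients also die sooner, part of any survival difference reflects who was operated on and not the operation.

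The data list is protocol content. It fixes what nine centres abstract from their charts. A separate analysis plan could add matching, weighting or adjustment, but none of these can use a field that was not collected. The open-ended ending of the demographic and anthropometric item does not naturally extend to performance status or comorbidity. Postoperative morbidity is an outcome in the surgical group, not a baseline measure.

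**Working it through.** **The plan's own figures.** With 5-year OS of 60% and 25%, the hazard ratio is ln 0.60 / ln 0.25 = 0.368, which matches the stated 0.37. Schoenfeld events at 90% power, two-sided 0.05 and a 0.15/0.85 split are (1.960 + 1.282)² / (0.15 × 0.85 × (ln 0.368)²) ≈ 83. The 5-year event probability is 0.85 × 0.75 + 0.15 × 0.40 = 0.6975, so N = 83 / 0.6975 ≈ 119, against 117 stated. The sample size reproduces closely and is not in dispute; it supplies the survival level and group split used below.

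**Inputs from the protocol.** Medical 5-year OS is 25%. The surgical share is 15%. There are nine centres (the sponsor centre and eight others) with 75–80 patients each, hence 675–720. I take 9 × 78 = 702, of whom 15% is 105 resected and 597 medical. Follow-up is cut at 5 years.

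**Assumed inputs, not in the protocol.** Surgery has no effect. Poor fitness is one binary factor, present in 5% of resected and in 20%, 30% or 40% of medical patients. It multiplies the hazard of death by G = 1.5, 2 or 3. Survival is exponential within each fitness class.

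**Worked case, 30% unfit and G = 2.** Choose the hazard h of fit patients so that medical OS is 25%: 0.70·exp(−5h) + 0.30·exp(−10h) = 0.25. With x = exp(−5h), 0.30x² + 0.70x − 0.25 = 0, so x = 0.3147 and h = 0.231 per year. Surgical 5-year OS is 0.95 × 0.3147 + 0.05 × 0.3147² = 0.304. The apparent hazard ratio is about ln 0.304 / ln 0.25 = 0.86.

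**All nine settings.** 4,000 simulated studies each. Each cell gives the apparent surgery hazard ratio from the log-rank one-step estimate, exp[(O−E)/V], and the share of studies with unadjusted log-rank p<0.05.

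| Hazard ratio for poor fitness | 20% of medical unfit | 30% | 40% |
|---|---|---|---|
| 1.5 | 0.95; 7% | 0.91; 12% | 0.88; 18% |
| 2 | 0.91; 11% | 0.86; 25% | 0.81; 44% |
| 3 | 0.88; 18% | 0.81; 45% | 0.74; 76% |

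Repeat runs of 1,500 studies agree within a few percentage points and put the last cell at 77–78%. The nominal rate is 5%. Surgical 5-year OS under these settings is 27% to 36%, against 25% in the medical group.

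**Sensitivity.** If 10% of resected patients are unfit, the 30%, G = 2 case gives 0.89 and about 16%.

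**What this does not show.** The simulation is of the unadjusted comparison. Residual bias after a Cox model with age, BMI and tumour burden was not computed.

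**The case against.** The strongest reply is that the protocol never says fitness decides who is resected. Its background discusses isolated versus systemic disease, and disease extent is collected in detail. This stands: the fitness link is a clinical inference, and a reader should not take it as a documented selection rule.

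A reader might also infer that enrolling 675–720 patients makes this bias likely to reach significance. The figures do not support that. Eight of the nine settings stay below 50%, and only the most extreme exceeds it. Nor could fitness alone explain an effect of the planned size: the lowest apparent hazard ratio above is 0.74, against 0.37.

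It is tempting to say that the information is lost once abstraction is done. Nothing in the protocol says the archives become unavailable, so a return to the charts is possible, at the cost of reopening them at each centre. It would also go too far to say that no planned analysis helps at all. Age and BMI are weak proxies, expert opinion can enter the Cox model, and excluding best supportive care or palliation removes some of the least fit. These reduce the confounding but do not replace a direct measure.

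Finally, about 500 of the 675–720 patients (500/720 = 69% to 500/675 = 74%) belong to the retrospective phase, where such fields may often be blank. That limits what the remedy can achieve there and shapes how it must be written. It does not justify leaving the fields out for everyone.

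**Conclusion.** The point holds as a gap in data collection that affects the primary comparison. No listed field measures baseline fitness, so the treatment effect cannot be adjusted for it directly. Under the assumed inputs the bias favours surgery in every setting: an apparent hazard ratio of about 0.95–0.74 when the true value is 1, with p<0.05 in about 7–78% of studies. At 30% unfit and a fitness hazard ratio of 2 it is about 0.86, with about 25%. Prevalence, fitness hazard ratio and the absence of a surgery effect are all assumptions, and the figures apply to the unadjusted log-rank comparison. The likely consequence is an inflated benefit or, less often, a false positive result. It is worth correcting because the remedy is cheap.

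**What to change.** - **Data list.** Under Variables and procedures, add performance status (ECOG or equivalent) and a comorbidity index, both dated at the treatment decision. Make them mandatory for prospective patients and abstract them from the archives where charted. Do not accept ASA class as a substitute: it is a pre-anaesthetic grade and would be recorded mainly in resected patients, so the scale used and its missingness would follow treatment.
- **Missing data.** Exempt the two fields from the Phase I condition of complete data and from the statement that missingness is below 5% throughout. Report their completeness by treatment group. A separate category for values not recorded would not remove confounding in those patients.
- **Analysis.** Keep both fields in the multivariable OS and RFS Cox models that include treatment, whatever their univariable p-value. Report the surgery hazard ratio with and without them in the patients who have them recorded. Collecting the fields does nothing for the log-rank test, which stays unadjusted, so the adjusted estimate must be shown beside it.
- **Sensitivity.** For patients without these fields, add a sensitivity analysis for unmeasured confounding, for example an E-value.

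The cost is some extra chart abstraction and a few sentences of specification, with no new procedure or patients. The drawback is that adjustment in the older archive patients will be only partial.
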